11.6 Safety and Exploratory Endpoints

- 1) Laboratory anomalies (Grade 3-5 AEs) as per the NIAID DAIDS toxicity grading table will be summarized for the incidence over 2 weeks of having at least one event and the mean number of events with cumulative incidence and linear regression models, respectively. If the cumulative incidence of a laboratory AE for any given anomaly (e.g. anemia, acute kidney injury) is >10%, the lab measurement will be individually summarized as a continuous variable. This is the key safety endpoint.
 - a) Grade 1-2 AEs will also be collected and summarized but are not the protocol scientific endpoint.
- 2) Clinical adverse events (Grade 3-5 AEs or SAEs) will be summarized via cumulative incidence function.
 - a) Note: Clinical AEs are listed separately from laboratory anomalies as lab AEs occur in the majority of this critically ill population with advanced AIDS and receiving IV AMB.
- 3) Tolerability will be assessed as the percent of received and tolerated doses versus total daily doses as a continuous variable for the experimental low-dose 5-FC and control standard dose 5-FC groups over the first two weeks.
 - a) Dropouts and study withdrawals will be summarized.
- 4) Descriptive analyses for the lower-dose 5-FC on pharmacokinetics of 5-FC concentrations in blood, CSF, and other bodily fluids/tissues; both antemortem and possibly postmortem.

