6.2.2 Flucytosine

Flucytosine (5-fluorocytosine) is a fluorinated pyrimidine that is available as 250mg and 500mg oral capsules. Flucytosine is a white crystalline powder and the following inactive ingredients: cornstarch, lactose, and talc.

Typical dosing is 100mg/kg/day divided in 6-hour intervals. Flucytosine is rapidly and virtually completely absorbed following oral administration.

Flucytosine is taken up by fungal organisms via the enzyme cytosine permease. Inside the fungal cell, flucytosine is rapidly converted to fluorouracil (5-FU) by the enzyme cytosine deaminase. Fluorouracil exerts its antifungal activity through the subsequent conversion into several active metabolites, which inhibit protein synthesis by being falsely incorporated into fungal RNA or interfere with the biosynthesis of fungal DNA through the inhibition of the enzyme thymidylate synthetase.

Acquisition: Any GMP-manufactured Flucytosine is acceptable.

[figure not shown]
Product Storage: Flucytosine should be stored at room temperature between 15-30°C.

Study administration:

Investigational cohort: Subjects enrolled will receive 10 days of flucytosine at 60mg/kg/day in 3 divided doses. Three divided doses are a general recommendation. Based on the number of tablets or GI tolerability, the number of doses can be altered. Table 6.2.2 provides an example approximate dosing schedule.

Table 6.2.2 Example Daily Dosing Regimen by Weight

Weight	Total 500mg Tablets Per Day	Pills per Dose	Mg/Kg Dose Range
<30	Weight based dosing	Respective pills every 8 hours	
30-38	4	2, 1, 1	54.1 - 66.7
38-44	5	2, 2, 1	56.8-65.8
45-53	6	2, 2, 2	55.6-66.7
54-62	7	3, 2, 2	56.2 - 64.8
63-70	8	3, 3, 2	57.5 - 63.5
71-79	9	3, 3, 3	57.0 - 63.4
80-87	10	4, 3, 3	57.5 - 62.5

88-94	11	4, 4, 3	58.5 - 62.5
95-103	12	4, 4, 4	58.3 - 63.2
>104	Weight based dosing		

Estimated weight is acceptable to use (e.g. in comatose or confused persons unable to stand on a scale). Dose should be adjusted once a measured weight is available. There is a general preference to round up when between weight bands or when in doubt.

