6.4 Assessment of Subject Adherence to Study Interventions

While subjects are hospitalized, study personnel (nurse or medical officer) will directly oversee administration of study medication to ensure compliance and record time of administration. Administration of antifungals will be by directly observed therapy while subjects are hospitalized during the first 1-2 weeks. Upon hospital discharge during outpatient management, self-reported adherence collected via a patient diary and pharmacy records will be used to assess study drug adherence. Patient diaries will include at minimum, the date the dose was taken, amount of dose administered, and number of doses taken in one day.

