9.8 Study Medication Discontinuation

This study medicine can be halted or interrupted if the investigator of record has concern of harm by the study drug. If the participant wishes to dose reduce due to intolerance of GI side effects (e.g. nausea), this is allowable. This is not a protocol deviation, but tolerability is an exploratory endpoint. The participant may discontinue the study medicine and remain in the study. Any dose reduction or discontinuation should be recorded on the 'Med CRF' for the study medicine. Before discontinuing the medication, the investigator should consider dividing the scheduled daily dose into smaller doses or dose reduction.

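### Section 11.6 does not define the unit or the denominator of tolerability, and no planned analysis summarises the mg/kg/day of 5-FC delivered

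*Combined protocol and SAP*

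**What the plan says.** Section 11.6, item 3, gives the measure: "Tolerability will be assessed as the percent of received and tolerated doses versus total daily doses as a continuous variable". It is to be computed for the "experimental low-dose 5-FC and control standard dose 5-FC groups over the first two weeks".

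The assigned regimen in Section 6.2.2 is: "Subjects enrolled will receive 10 days of flucytosine at 60mg/kg/day in 3 divided doses". The same section allows the schedule to change ("Based on the number of tablets or GI tolerability, the number of doses can be altered") and, for tablet counts, adds: "There is a general preference to round up when between weight bands or when in doubt". It also says the dose should be adjusted once a measured weight is available.

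Section 9.8 allows reduction: "If the participant wishes to dose reduce due to intolerance of GI side effects (e.g. nausea), this is allowable". It continues: "This is not a protocol deviation, but tolerability is an exploratory endpoint". Before stopping the drug, the investigator is to consider splitting the daily dose or reducing it. Section 5.5 says instead that alterations in dose count as a protocol deviation, and that adjustments are documented and reported to the IRB.

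Amounts are recorded. Section 9.8 puts reductions and discontinuations on the Med CRF. Section 6.4 has inpatient dosing directly observed, and for outpatients: "Patient diaries will include at minimum, the date the dose was taken, amount of dose administered, and number of doses taken in one day".

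**The concern.** Section 9.8 excuses GI-driven reductions from deviation status and points to the tolerability endpoint in the same sentence, so that endpoint is where such reductions should show. If it counts administrations, a smaller dose taken on schedule leaves no trace in the score, and splitting the daily amount changes the number of doses without changing the drug received.

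Tolerability at the reduced dose is part of a secondary objective (Section 3.1.2) and of the hypothesis (Section 11.3). A group mean near 100% would be read as good tolerance of 60 mg/kg/day, although some participants might have received well under that amount.

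The reader of the EFA result also needs to know what dose was actually given. Section 7.2 admits participants after up to 2 days of standard-dose 5-FC, Section 5.5 allows a move to standard dose after stopping the low dose, and Section 11.1 analyses everyone by intent to treat. No listed analysis reports the resulting mg/kg/day.

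**Working it through.** **1. The plan's own figures (Table 6.2.2).** Formula: mg/kg/day = tablets × 500 / weight. All nine printed maxima reproduce at the lower edge of their rows, and five of nine printed minima reproduce at the upper edge. The other four are:

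| Row (kg) | Tablets | Printed minimum | At labelled upper edge |
|---|---|---|---|
| 30-38 | 4 | 54.1 | 2000/38 = 52.6 (54.1 is 2000/37) |
| 45-53 | 6 | 55.6 | 3000/53 = 56.6 (55.6 is 3000/54) |
| 54-62 | 7 | 56.2 | 3500/62 = 56.5 |
| 63-70 | 8 | 57.5 | 4000/70 = 57.1 |

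A weight of 38 kg is in two rows, giving 2000/38 = 52.6 or 2500/38 = 65.8 mg/kg/day (ratio 1.25). A weight of 104 kg is in none: the last band ends at 103 and the next row starts above 104.

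**2. What dose means in the text.** It means an administration in Section 5.3.2 (consent before a stated number of 5-FC doses), Section 6.2.2 (three divided doses, whose number can change), Section 6.4 (the diary lists amount and number of doses separately) and Section 7.2 (counting 5-FC doses). It means an amount where Section 9.8 speaks of dividing the scheduled daily dose, and where the synopsis rationale speaks of lowering the daily dose. The count reading is the more natural one but is not certain.

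**3. Count score against milligram score.** Take a 50 kg participant on 6 tablets a day (2, 2, 2). That is 3,000 mg/day, or 3000/50 = 60 mg/kg/day; 3 × 10 = 30 administrations; and 3000 × 10 = 30,000 mg. Every administration is taken and tolerated. Halving is an illustration; the documents name no size of reduction.

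| Scenario | Count score | mg received | mg score | mg/kg/day over 10 days |
|---|---|---|---|---|
| Full dose | 30/30 = 100% | 30,000 | 100% | 60 |
| Halved from day 1 | 30/30 = 100% | 10 × 1500 = 15,000 | 50% | 30 |
| Halved from day 4 | 30/30 = 100% | 3 × 3000 + 7 × 1500 = 19,500 | 65% | 39 |
| Halved from day 6 | 30/30 = 100% | 5 × 3000 + 5 × 1500 = 22,500 | 75% | 45 |
| Full amount in 6 doses a day | 60/60 = 100%, or 60/30 = 200% if the denominator stays at 30 | 30,000 | 100% | 60 |

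The milligram scores use the assigned amount as denominator. With the currently prescribed amount as denominator, the three halved participants would score 100% in milligrams too, so the reference must be stated as well as the unit.

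**4. Delivered dose with standard-dose 5-FC included.** Section 6.2.2 gives typical dosing as 100 mg/kg/day.
- Two days at 100, then ten at 60: (200 + 600)/12 = 66.7 mg/kg/day. Over the first seven of those days: (200 + 300)/7 = 71.4.
- Five days at 60, then five at 100 (the switch day is assumed): (300 + 500)/10 = 80.0.

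The documents do not say how often either will occur.

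**5. Planned analyses.** Sections 11.4 to 11.6 list EFA, DOOR, CSF sterility, survival, laboratory and clinical adverse events, tolerability, and descriptive pharmacokinetics. None summarises milligrams or mg/kg/day received.

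**6. Deviation status.** Section 5.5 treats any alteration in dose as a deviation. Section 9.8 says a GI-driven reduction is not one. Both cannot apply to the same reduction.

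**The case against.** The strongest reply is that the count reading is assumed. The denominator could be a daily amount, and because Section 9.8 ties reductions to this endpoint, the authors may have meant reductions to lower the score. With assigned milligrams as denominator, the participant halved from day 1 scores 50%. This stands as far as it goes: the defect is an undefined measure, not a proven count. Either reading needs the definition written down.

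Second, the words on tolerated doses may catch a dose that was vomited before the reduction. That also stands. A score of 100% requires that no administration was classed as untolerated, and the plan does not say how that is judged.

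Three stronger readings are tempting, and the documents do not support them.
- A reader might infer that the dose given is never measured. It is: on the Med CRF, by observed dosing and in diaries. Section 11.1 puts all collected data in listings, and Section 4.2 provides for 5-FC concentrations. What is missing is a planned summary of mg/kg/day.
- A reader might infer from the preference to round up that delivered doses drift far toward the control dose. That would need participants dosed a full band too high, which the instruction to adjust to measured weight limits. The between-band case is small: 44.5 kg on 6 tablets gives 3000/44.5 = 67.4, against a printed maximum of 66.7. Rounding up does not affect a percentage of doses at all.
- A reader might count planned doses in the two groups and infer a built-in imbalance. The documents do not state the number of 5-FC days for the liposomal arm of the control trial, and any difference in course length would persist in a milligram ratio.

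**Conclusion.** The concern holds as a minor point. Section 11.6 leaves both the unit and the reference of tolerability open. On the natural reading, a participant can score 100% on half the assigned milligrams. Delivered mg/kg/day, the exposure the trial makes its claim about, is recorded but not summarised in any planned analysis.

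The 50%, 65% and 75% figures rest on an illustrative halving with every administration tolerated. The frequency of reductions is unknown, so no effect on the group mean can be given. The conclusion rests on the text supplied; Section 11.3 defers details of the historical comparison to an SAP.

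A reader might infer that a non-inferior EFA result is thereby invalid. That does not follow. Tolerability is called exploratory, is absent from the endpoint list in Section 3.2, and enters no test or sample size; redefining it leaves the intent-to-treat EFA comparison unchanged. Delivered dose would help interpret that result, not alter it.

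The inconsistencies in Table 6.2.2, and the conflict between Sections 5.5 and 9.8, are on the face of the text and need reconciling. This review takes no view on which dose or rule is right.

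**What to change.** - Define tolerability as cumulative mg of 5-FC received and tolerated, divided by cumulative mg assigned. The denominator is assigned mg/kg/day × measured weight × planned days while alive and in follow-up, computed by group. Count reductions and stops for intolerance as shortfall, and state how a dose is judged not tolerated.
- Report deaths and renal dose adjustments separately, so that they are not scored as intolerance. Table 2.2 gives 18/222 = 8.1% two-week mortality in Ugandans with GCS 15, and Section 6.2.2 calls for dose adjustment in renal insufficiency.
- Beside the EFA result, as descriptive context, report delivered mg/kg/day (median, range), including standard-dose 5-FC given before enrolment or after discontinuation, and the proportion with any reduction.
- Reconcile Table 6.2.2 so that each weight falls in one row and each printed range matches its bounds. Reconcile Sections 5.5 and 9.8 on whether a dose reduction is a deviation.

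The cost is SAP wording, one derived variable from records already planned, and two text corrections. The downside is on the control side: if the historical records hold only dose counts, the milligram measure is available for the trial cohort alone, and the count measure is kept for the between-group comparison, with its unit and denominator stated.

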11.7 Statistical Power for Secondary Outcomes

Secondary endpoints are primarily descriptive in nature without statistical power for individual dose comparison unless the effect size is large.

12. ETHICS/PROTECTION OF HUMAN SUBJECTS

12.1 Ethical Standard

This study is to be conducted according to US and international standards of Good Clinical Practice (International Conference on Harmonization guidelines), Declaration of Helsinki, and

International Ethical Guidelines for Biomedical Research Involving Human Subjects, applicable government regulations for Uganda, U.S., international and Institutional research policies and procedures. All investigators must have received human subject protection and Good Clinical Practice training prior to human subject involvement.

12.2 Institutional Review Board

Prior to the initiation of the study at the clinical research site, the protocol, all informed consent forms and the participant Information materials will be submitted to and approved by the local IRB of record. Likewise, any future amendments to the study protocol will be approved by each site's IRB.

This protocol and any amendments will undergo review and approval by the local site IRB in Kampala, Uganda and the Uganda National Council of Science and Technology (UNCST) under FWA00001293, University of Minnesota (FWA00000312), and all other relevant local/national IRBs for any clinical site.

12.3 Informed Consent Process

Informed consent is a process that is initiated prior to the individual's agreeing to participate in the research study and continuing throughout the individual's study participation. Extensive discussion of risks and possible benefits of this therapy will be provided to the subjects and their families. Consent forms describing in detail the study interventions/products, study procedures, and risks are given to the subject and written documentation of informed consent is required prior to enrollment and starting the study product. Consent forms will be IRB-approved, and the subject will be asked to read and review the document. Upon reviewing the document, the investigator will explain the research study to the subject and answer any questions that may arise. The subjects will sign the informed consent document prior to any procedures being done specifically for the study. Procedures being performed for standard medical care (e.g., lumbar puncture, CSF diagnostic testing) may be performed prior to informed consent. Meningitis is a medical emergency, and routine medical care should not be withheld, endangering potential participants.

The subjects should have the opportunity to discuss the study with their surrogates or think about it prior to agreeing to participate. The subjects may withdraw consent at any time throughout the course of the trial. A copy of the informed consent document will be given to the subjects for their records. The rights and welfare of the subjects will be protected by emphasizing to them that the quality of their medical care will not be adversely affected if they decline to participate in this study.

12.4 Subject Confidentiality

Subject confidentiality is strictly held in trust by the participating investigators, their staff, and the sponsor(s) and their agents. This confidentiality is extended to cover testing of biological samples and genetic tests in addition to the clinical information relating to participating subjects.

The study protocol, documentation, data, and all other information generated will be held in strict confidence. No information concerning the study, or the data will be released to any unauthorized third party without prior written approval of the sponsor. For research uses, all data will be de-identified and coded with the clinic medical record number.

Protected health information will only be shared through a secure network and will not be used or sent through WhatsApp, Zoom, or email.

Any authorized representatives of the sponsor may inspect all documents and records required to be maintained by the investigator, including but not limited to, medical records (office, clinic, or hospital) and pharmacy records for the subjects in this study. The clinical study site will permit access to such records.

Subject confidentiality is strictly held in trust by the participating investigators, their staff, and the sponsor(s) and their agents. This confidentiality is extended to cover testing of biological samples and genetic tests in addition to the clinical information relating to participating subjects.

The study protocol, documentation, data, and all other information generated will be held in strict confidence. No information concerning the study, or the data will be released to any unauthorized third party without prior written approval of the sponsor. For research uses, all data will be de-identified and coded with the clinic medical record number.

Any authorized representatives of the sponsor may inspect all documents and records required to be maintained by the investigator, including but not limited to, medical records (office, clinic, or hospital) and pharmacy records for the subjects in this study. The clinical study site will permit access to such records.

12.5 Study Discontinuation

In the event that the study is discontinued, subjects remain eligible for ART according to national guidelines and as provided by PEPFAR, Global Fund, or Ministry of Health sources. Participants will be encouraged to continue to receive ART from the outpatient clinic or referred to a clinic of their choice for ongoing HIV care and management of CM.

12.6 Future Use of Stored Specimens

According to Ugandan regulations, a separate informed consent for long term storage of samples for future research testing is necessary. The "SCREENING STORAGE CONSENT FORM FOR MENINGITIS" asks for consent for long term storage of samples. Subjects have the option to consent for long term storage of samples for this study only and/or for future research. If a subject declines storage consent, this will be noted on their lab order entry form and in their study chart, and specimens will be discarded after appropriate clinical testing is completed. The purpose of the long-term storage is to enable: 1) future diagnostic testing for assays which are not currently commercially available (e.g., multi-band semi-quantitative CrAg LFA; new TB tests); 2) pathogenesis studies to better understand immunology and microbiology of cryptococcal meningitis in relation to clinical outcome; 3) pharmacokinetic studies of antifungal medications; 4) antifungal susceptibility testing of *Cryptococcus* isolates.

There will not be a separate storage informed consent form for the FLOOR study. However, all FLOOR participants will be co-enrolled in the ongoing COAST observational study. This study includes a separate storage informed consent form.

13. DATA HANDLING AND RECORD KEEPING

The investigator is responsible to ensure the accuracy, completeness, legibility, and timeliness of the data reported. All source documents should be completed in a neat, legible manner to ensure accurate interpretation of data. Black ink is required to ensure clarity of reproduced copies. When making changes or corrections, cross out the original entry with a single line, and initial and date the change. DO NOT ERASE, OVERWRITE, OR USE CORRECTION FLUID OR TAPE ON THE ORIGINAL.

Copies of the CRF will be provided for use as source documents and maintained for recording data for each subject enrolled in the study. Data reported in the CRF derived from source documents should be consistent with the source documents or the discrepancies should be explained.

13.1 Source Documents

Source data are all information, original records of clinical findings, observations, or other activities in a clinical trial necessary for the reconstruction and evaluation of the trial. Source data are contained in source documents. Source data are all information, original records of clinical findings, observations, or other activities in a clinical trial necessary for the reconstruction and evaluation of the trial. Examples of these original documents and data records include, but are not limited to, research charts, laboratory notes, memoranda, pharmacy dispensing records, recorded data from automated instruments, copies or transcriptions certified after verification as being accurate and complete, media, x-rays, and subject files and records kept at the pharmacy, at the laboratories, and medico-technical departments involved in the clinical trial.

The research team are the primary healthcare providers for participants after they enter into the trial and will manage all routine care for the participants. The research team will work together with the hospital team for complete hospital management and the hospital clinical team will be involved for emergent and urgent needs of the participant when the research team is not available or actively providing care on the wards.

The Daily Clinical Review form will serve as the source for clinical observations obtained by the study team, as this is the first location where data are recorded. During outpatient visits, CRFs are completed first with information then transcribed into the electronic medical record.

Study data forms will be digitally scanned for permanent record keeping and for enabling rapid resolution of any discrepancies.

The site will maintain appropriate medical and research records for this trial, in compliance with ICH E6, Section 4.9 and regulatory and institutional requirements for the protection of confidentiality of subjects.

Information Type	Source Document	Rationale / Record Location
Lab Values	Paper Lab Report	In Research chart
Microbiology Values	Paper Lab Report	In Research chart
CSF CrAg Bedside Test	Screening CRF	CrAg testing is performed at bedside by trained study staff and the results are recorded on a CRF
Pregnancy Test	CRF	Point-of-care pregnancy test is performed by study staff in the hospital, recorded on the CRF
Medical History	Screening CRF and Meningitis CRF	Past medical history is obtained directly from the patient and recorded on the Screening and Meningitis CRFs. Hospital Records are not used.
Physical Exam, or Clinical Observations	Daily Clinical Review Form	Clinical observations are recorded directly in the Daily Clinical Review Form. Hospital records are not used and are not the source document.
Study Medicine Dispensing	Pharmacy Dispensing Log	Research Pharmacy in locked file cabinet
Study Medication Administration	Daily Clinical Review Form and Nurses Notes; Participant Adherence Diary	Research staff record study medication administration on daily clinical review forms and nurses notes while participant is in hospital; Participants self-report study medication administration after hospital discharge in a patient adherence diary.
Concomitant Medications	Med CRF	Research team prescribes all medications. Medications are recorded on Med CRF by the prescribing provider.
Clinical Adverse Events	AE Log	Research staff record AEs on the AE Log. Participants contact research study team for all their health care needs. (Given 24/7 contact phone numbers and reimbursed for transport costs for scheduled or sick visits). All healthcare once enrolled is provided without cost (within reasonable relatedness to HIV, meningitis, or any AE).
Lab Adverse Events	Paper Lab Report	In Research chart

